6.1.2 Inclusion criteria for subjects with moderate to severe chronic plaque PSO

5. Have a diagnosis of chronic plaque PSO for at least 6 months.
6. Baseline PASI ≥ 12 and BSA affected by PSO $\geq 10\%$ and PGA score of 3 or higher.
7. Candidates for systemic PSO therapy and/or phototherapy and/or chemophototherapy.

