14.3.2 Other efficacy analyses

14.3.2.1 Analysis of the secondary efficacy variables for subjects with moderate to severe chronic plaque PSO

The secondary efficacy variables will be analyzed for all subjects in the FAS.

Secondary efficacy variables are PASI90, PGA response, and change from Baseline in DLQI at Week 16.

A subject will be classified as a PGA responder if the PGA is Clear or Almost clear with at least a 2-category improvement relative to Baseline. The analysis of PASI90 and PGA response at Week 16 will be analyzed for treatment effects using pairwise comparisons based on the same method as that for the primary efficacy variable.

The MCMC algorithm is based on the multivariate normal model; imputed values for PGA will not generally be one of the discrete values actually used in PGA scoring (0, 1, 2, 3, or 4).

Therefore, standard rounding rules will be applied to the imputed values in order to derive the binary PGA response variable. For example, if a subject has a PGA score imputed as 1.4 (and assuming a Baseline PGA score of 3), this imputed value would be rounded down to 1, and the minimum change from Baseline of 2 would have been met. Therefore, this subject would be considered a responder.

The significance testing of each CZP treatment group vs PBO will be part of the fixed sequential testing procedure described in Section 14.2.

The analysis of DLQI will be based on the change from Baseline at Week 16. Treatment group comparisons for each CZP treatment group vs PBO will be performed using an analysis of covariance (ANCOVA) model with treatment group and prior biologic exposure (yes/no) as factors and Baseline DLQI score as a covariate. The treatment differences and corresponding 97.5% confidence intervals will be calculated based on the adjusted means. Missing values will be imputed using last observation carried forward (LOCF). Each CZP dose will be compared against PBO to establish superiority over PBO and will be tested at an alpha of 0.025 as part of the fixed sequence testing procedure described in Section 14.2.

14.3.2.2 Analysis of the other efficacy variables for subjects with moderate to severe active plaque PSO

All other efficacy variables (eg, PASI50, PASI75, PASI90, PASI100, PGA, MCID) will be analyzed for all subjects in the FAS.

All categorical variables (eg, PASI score, PGA score, BSA score, DLQI) will be summarized using frequency tables by each visit.

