Treatment group comparisons for each CZP treatment group vs placebo will be performed using an analysis of covariance (ANCOVA) model with treatment group and prior biologic exposure as factors and Baseline DLQI score as a covariate. The least squares (LS) means and standard errors derived from the model will be presented for each treatment group. Additionally, adjusted mean treatment differences, corresponding confidence intervals, and p-values will be reported. Missing values will be imputed using LOCF.

A line plot will be generated to present adjusted mean change from Baseline in DLQI by randomized treatment group through Week 16.

Percent of subjects achieving MCID or DLQI remission

At a given visit, a subject will be considered to have achieved MCID if their individual improvement from Baseline score is ≥ 4 . A 4-point improvement in the DLQI score (DLQI response) has been reported to be meaningful for the subject.

At a given visit, a subject will be considered to have achieved remission if their absolute DLQI score is ≤ 1 .

Initial Period

DLQI MCID responder rates and subjects with DLQI remission will be summarized by visit and randomized treatment group for the FAS and CFAS. Missing data will be imputed using NRI. A summary of corresponding results based on observed cases will be provided by visit and randomized treatment group for the FAS and CFAS.

A comparison between treatment groups vs Placebo will be made at each time point using logistic regression models based on NRI imputed data and observed data. The estimate for the responder rate, the odds ratio, 95% CI, and p-value from the model will be presented.

Maintenance Period

For the maintenance phase, MCID responder rates and subjects with DLQI remission will be summarized by visit and blinded maintenance treatment group for the FAS and CFAS. Missing data will be imputed using NRI. Additionally, a summary of corresponding results based on observed cases will be provided by visit and (blinded) maintenance treatment group for the FAS and CFAS, and by escape maintenance treatment group for the FAS.

8.3.8 Change from Baseline in Itch Numeric Rating Scale, percent of subjects achieving MCID or remission

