At each post Baseline visit, the change from Baseline in Itch Numeric Rating Scale and percent of subjects achieving minimal clinically important difference (MCID) or remission, will be reported. See [Section 8.2.4](#) for the derivation of the change from Baseline in Itch Numeric Rating Scale.

Change from Baseline in Itch Numeric Rating Scale

The approach for summarizing the actual and change from Baseline scores over time in Itch Numeric Rating Scale for the Initial Period and the Maintenance Period on observed and LOCF imputed cases will follow the same approach as used for summarizing PASI scores, described in [Section 0](#). Percent change from Baseline will not be summarized, but results based on LOCF on CFAS will be provided. A line plot will be generated to present change from Baseline in itch severity by randomized treatment group through Week 16.

Percent of subjects achieving MCID, or remission

At a given visit, a subject will be considered to have achieved MCID if their individual improvement from Baseline score is ≥ 4 . A 4-point improvement in the Itch Numeric Rating Scale has been reported to be meaningful for the subject.

At a given visit, a subject's remission is defined as reaching an Itch Numeric Rating Scale of zero.

The summary of the results for subjects achieving MCID or Itch Numeric Rating Scale remission will be done analogous to analysis described in [Section 8.3.7](#).

8.3.9 ACR20, 50, 70 response criteria and change from Baseline in all individual ACR core components

For subjects with psoriatic arthritis (PsA), the American College of Rheumatology 20%/50%/70% response criteria (ACR20, ACR50, and ACR70) will be evaluated. The analysis will be based on the PsA Set and on the PsA Set including only subjects with 3 or more tender joints and 3 or more swollen joints at Baseline.

A subject will be considered an ACR20/50/70 responder if:

The counts for both tender joint count (TJC) and swollen joint count (SJC) (68/66 joint counts) ([Section 8.3.10](#)) have reduced by 20/50/70% or more, respectively, from the Baseline assessment

and

There is a 20%, 50%, 70% or greater improvement in at least 3 of the 5 remaining core set measures:

- Physician's Global Assessments of Disease Activity (PhGADA, [Section 8.3.11](#))
- Patient's Global Assessments of Disease Activity (PGADA, [Section 8.3.12](#)),
- Patient's Assessment of Arthritis Pain (PAP, [Section 8.3.13](#)),

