8.3.14 Health Assessment Questionnaire Disability Index score

The Health Assessment Questionnaire-Disability Index (HAQ-DI) contains 20 items divided into 8 domains that measure: dressing and grooming, arising, eating, walking, hygiene, reach, grip, and common daily activities. Subjects are required to indicate the degree of difficulty they have experienced in each domain in the past week on a 4-point scale that ranges from 0 (without difficulty) to 3 (unable to do). Any individual score of less than 2 is adjusted to 2 if the activity requires assistance from another individual or the use of an assistive device. The

highest score in each category is then summed (0 to 24) and divided by the number of categories scored to give a score that ranges from 0 to 3 (Matsuda et al, 2003).

If the patient does not provide an answer for any questions within a category, no score will be provided for that category. The HAQ disability index will be calculated by dividing the sum of the category scores by the number of categories with at least 1 question answered. If fewer than 6 categories have responses, no disability score will be calculated. A lower HAQ disability score indicates an improvement in function.

Percent of subjects achieving HAQ-DI MCID

At a given visit a subject will be considered to have the minimum clinically important difference in HAQ-DI for PSA subjects if the difference is ≥ 0.3 points (Meese, 2009). Tables will present Observed case and NRI imputed data.

For further details for the analysis of this data, please refer to Section 8.3.9.

Additionally, a line plot will be generated to present change from Baseline in HAQ-DI score by randomized treatment group through Week 24/52.

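### DLQI, itch and HAQ-DI MCID response counts subjects whose Baseline is too low to reach the threshold, so rates and CZP-placebo contrasts are diluted by an unknown amount

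*SAP*

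**What the plan says.** **Thresholds.** For DLQI and Itch NRS, SAP 8.3.7 and 8.3.8 use the same rule: "a subject will be considered to have achieved MCID if their individual improvement from Baseline score is" 4 or more. The stated grounds are that "A 4-point improvement in the DLQI score (DLQI response) has been reported to be meaningful for the subject" and that "A 4-point improvement in the Itch Numeric Rating Scale has been reported to be meaningful for the subject". For HAQ-DI, SAP 8.3.14 says a subject has the "minimum clinically important difference in HAQ-DI for PSA subjects if the difference is" at least 0.3 points, without giving a direction in that sentence.

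**Populations.** SAP 8.3.7: "DLQI MCID responder rates and subjects with DLQI remission will be summarized by visit and randomized treatment group for the FAS and CFAS". For itch, the summary of MCID or "Itch Numeric Rating Scale remission will be done analogous to analysis described in" 8.3.7. Protocol 14.3.2.2 agrees for the plaque population: "PASI100, PGA, MCID) will be analyzed for all subjects in the FAS". HAQ-DI MCID gets observed-case and NRI tables and is otherwise referred to SAP 8.3.9, which uses the PsA Set and its subset with at least 3 tender and 3 swollen joints at Baseline.

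**Comparisons.** For DLQI and itch, SAP 8.3.7 plans logistic regression against placebo at each Initial Period visit, on NRI and observed data, reporting responder rate, odds ratio, 95% CI and p-value. It names no Baseline-score covariate; SAP 4.1 gives that covariate only to the DLQI and itch score analyses. The responder comparison in SAP 8.3.9 is a Wald test of a difference in proportions.

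**Entry.** Protocol 6.1.2 sets severity minima for PASI, BSA and PGA ("PGA score of 3 or higher"). Nothing sets a minimum for DLQI, itch or HAQ-DI.

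**The concern.** DLQI runs from 0 to 30, itch from 0 to 10 and HAQ-DI from 0 to 3, with 0 the best score on each. A subject with Baseline DLQI or itch of 0 to 3 cannot improve by 4. A subject with HAQ-DI below 0.3 (0, 0.125 or 0.25 when all eight categories are scored) cannot improve by 0.3. These subjects are non-responders at every visit whatever the treatment does.

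The reported rate then mixes two things: how often treatment produces a meaningful improvement, and how many subjects had room for one. Elsewhere the SAP attends to attainability. Section 8.2.1 notes that the entry PGA makes the 2-category improvement automatic for anyone reaching 0 or 1, mNAPSI is confined to subjects with nail disease, and joint outcomes also get a subset with enough affected joints. MCID has no such provision.

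At stake is the interpretation of rates, odds ratios and nominal p-values for patient-reported outcomes that will be read as treatment benefit.

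**Working it through.** **The plan's own figures.** The documents state no MCID rate, difference or power, so there is no MCID figure to reproduce. The only design figure, PASI75 power in Protocol 14.8.1, does reproduce: for 70% vs 15% at two-sided 0.025, 43 vs 22 subjects give 0.993 (pooled normal) or 0.986 (Fisher exact) against at least 98% stated. The MCID point does not bear on it.

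**Inputs.**
- Arm sizes 50 (each CZP dose) and 25 (placebo): Protocol 14.8.1. They illustrate DLQI and itch in the FAS; they do not describe the PsA Set.
- q, the share of each arm starting below the threshold: not in the documents; assumed, 0 to 30%.
- pC and pP, the MCID rates among subjects able to respond: not in the documents; assumed 70% vs 15% (borrowed from the PASI75 assumptions) and 70% vs 30%.

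**Formulas, with equal q in both arms as expected under randomization.**
- All-subject rate = p(1-q).
- Rate difference = (1-q)(pC - pP).
- Odds ratio = (pC/pP) x [1 - pP(1-q)] / [1 - pC(1-q)]. If pC > pP this falls as q rises. The risk ratio pC/pP is unchanged.

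**Results, 70% vs 15%.**

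| q | CZP | Placebo | Difference (points) | Odds ratio |
|---|---|---|---|---|
| 0 | 70.0% | 15.0% | 55.0 | 13.2 |
| 10% | 63.0% | 13.5% | 49.5 | 10.9 |
| 20% | 56.0% | 12.0% | 44.0 | 9.3 |
| 30% | 49.0% | 10.5% | 38.5 | 8.2 |

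Example at q = 20%: (0.56/0.44) / (0.12/0.88) = 1.273/0.136 = 9.3.

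**Results, 70% vs 30%.** The difference falls from 40.0 to 36.0, 32.0 and 28.0 points at q = 10%, 20% and 30%; the odds ratio falls from 5.4 to 4.6, 4.0 and 3.6.

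**Does restriction cost power?** Two-proportion normal approximation with pooled null variance, two-sided 0.05, q = 20%, 70% vs 30% among those able to respond:
- all subjects, 50 vs 25, 56% vs 24%: power 0.77;
- restricted, 40 vs 20, 70% vs 30%: power 0.86.

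Under these assumptions the smaller set has more power.

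**Chance imbalance in q.** The SD of the imbalance in floor share is sqrt[q(1-q)(1/50 + 1/25)] = 7.3, 9.8 and 11.2 points at q = 10%, 20% and 30%. Its contribution to the rate difference is smaller: sqrt[pC² q(1-q)/50 + pP² q(1-q)/25] = 3.1, 4.1 and 4.7 points for 70% vs 15%. The ordinary binomial standard error already contains it: at q = 20%, sqrt(0.56 x 0.44/50 + 0.12 x 0.88/25) = 9.6 points.

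**The case against.** The strongest reply is that this is a choice of estimand. The proportion of all treated, assessed subjects who gain the threshold is a legitimate quantity, the protocol asks for it in the FAS, and SAP 4.6 ties the FAS to the intention-to-treat principle. The comparison remains randomized and the dilution runs toward no effect. MCID is among the other efficacy variables, with no multiplicity adjustment (SAP 8.3). The DLQI and itch conclusions rest mainly on change-from-Baseline ANCOVAs with Baseline score as covariate. All of that stands. It is why the planned analysis should stay and why this is an improvement, not a correction of an invalid test. It does not remove the dilution from the rates and odds ratios that will be reported.

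Some stronger readings are tempting, and the documents do not support them:
- **A large loss.** Nothing shows that 10% to 30% of subjects start below the threshold, and entry requires substantial skin disease.
- **A logistic model for HAQ-DI.** None is planned; 8.3.14 plans tables and refers to 8.3.9.
- **A diluted placebo contrast in the CFAS.** That cohort has no placebo arm, so only its rates are affected.
- **Chance imbalance as a separate 7 to 11 point error.** That is the spread of the floor share, not of the result.
- **Remission as the mirror-image fault**, because a subject already at DLQI 1 or less, or itch 0, counts. Remission is defined as an absolute state, so counting such subjects follows the definition.
- **Replacing the all-FAS denominator.** Table 8-4 puts DLQI and itch MCID in the Week 24 interim analysis, and SAP 9.3 and 12.2 show this version was written with interim results known. Demoting the planned result now would be a post-hoc change.

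**Conclusion.** The point holds as a limited one. Subjects with Baseline DLQI or Itch NRS below 4, or HAQ-DI below 0.3, are counted as MCID non-responders although they cannot respond. If any such subjects exist, the rates are lower than among subjects able to respond. If CZP is better than placebo among those able to respond, the expected rate difference shrinks by the factor (1-q) and the odds ratio moves toward 1. That direction is certain in expectation; in a single trial, chance imbalance in q can mask it. The size depends wholly on q and on MCID rates that the documents do not give, so the tabulated figures are illustrations. For HAQ-DI the same logic applies within the PsA Set, whose size is not stated. Primary and key secondary conclusions are unaffected.

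**What to change.** 1. In SAP 8.3.7, 8.3.8 and 8.3.14, add MCID analyses restricted to subjects with Baseline DLQI of at least 4, Itch NRS of at least 4, or HAQ-DI of at least 0.3, using for each variable the method already planned. Baseline is measured before treatment, so the randomized comparison is kept.
2. Show, per arm, the number of subjects at or above the threshold, so that the reader can see q.
3. Keep the protocol's all-FAS analysis and the planned PsA Set tables as they are.
4. State in SAP 3.9 that the restricted analyses were added after the interim.
5. Word the HAQ-DI rule as a decrease from Baseline of at least 0.3; the section already says that a lower score is better.
6. Leave the remission definitions unchanged.

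Cost: a denominator flag, a few lines of SAP text and one more set of tables. The restricted analyses have fewer subjects.

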8.3.10 Swollen and tender joint counts (66/68 joints evaluation)

The following 68 joints are to be examined for tenderness by the Principal Investigator, another delegated physician, or an appropriately qualified medical professional (based on local requirements) who has had documented training on how to perform these assessments correctly. Preferably the same assessor should evaluate the subject at each arthritis assessment.

- Upper body (6): bilateral temporomandibular, sternoclavicular, and acromioclavicular joints
- Upper extremity (34): bilateral shoulders, elbows, wrists (includes radiocarpal, and carpal and carpometacarpal bones considered as a single unit), metacarpophalangeals (MCP I, II, III, IV and V), thumb interphalangeals (IP), proximal interphalangeals (PIP II, III, IV and V) and distal interphalangeals (DIP, II, III, IV, and V)
- Lower extremity (28): bilateral hips, knees, ankles, tarsi (includes subtalar, transverse tarsal, and tarsometatarsal considered as a single unit), metatarsophalangeals (MTP I, II, III, IV, and V), great toe interphalangeals, and proximal and distal interphalangeals (PIP II, III, IV, and V)

TJC is the sum of tender joints among the 68 joints. It ranges from 0 to 68.

The assessment for swelling is made on 66 joints from the above list. The hip joints are excluded. Artificial and ankylosed joints are excluded from both tenderness and swelling assessments.

SJC is the sum of swollen joints among the 66 joints. It ranges from 0 to 66.

Table 8–5: Swelling and tenderness grading

Grade	Swelling response (66)	Tenderness response (68)
0	None	None (not tender)
1	Detectable	Positive (tenderness)

If there are missing observations for tender or swollen joints then, for derivation of the tender or swollen joint count, the remaining observations will be assessed and weighted by dividing by the number of non-missing and by multiplying by 68 for the tender joint count and by 66 for the swollen joint count. If a joint is not evaluable at Baseline, then that joint is set to missing throughout the study.

For the analysis of this data, please refer to Section 8.3.9.

8.3.11 Physician's Global Assessment of Disease Activity (PhGADA, VAS)

The Investigator will assess the overall status of the subject with respect to their PsA signs and symptoms and functional capacity (considering both joint and skin components) using a VAS where 0 is “very good, asymptomatic and no limitation of normal activities” and 100 is “very poor, very severe symptoms which are intolerable and inability to carry out all normal activities.”

For the analysis of this data, please refer to Section 8.3.9.

8.3.12 Patient's Global Assessment of Disease Activity (PGADA, VAS)

Subjects will score their Global Assessment of Disease Activity in response to the question, “Considering all the ways your arthritis affects you, please mark a vertical line on the scale below to show how you are feeling today”, using a VAS where 0 is “very good, no symptoms” and 100 is “very poor, severe symptoms.” The subject should be asked to consider both joint and skin components in their response to this question.

For the analysis of this data, please refer to Section 8.3.9.

8.3.13 Patient's Global Assessment of Arthritis Pain (PGAAP, VAS)

For subjects with psoriatic arthritis (PsA), the Patient's Assessment of Arthritis Pain VAS is part of the ACR core set of measures in arthritis (Felson et al, 1993).

The Pain VAS consists of a horizontal line 100mm in length on which subjects are asked to indicate the level of their arthritis pain at the day of the visit between 0 (“no pain”) and 100 (“most severe pain”), in response to the question: “Please mark a vertical line on the scale below to show how much pain you have from your arthritis today” (Dworkin et al, 2008).

For the analysis of this data, please refer to Section 8.3.9.

8.3.14 Health Assessment Questionnaire Disability Index score

The Health Assessment Questionnaire-Disability Index (HAQ-DI) contains 20 items divided into 8 domains that measure: dressing and grooming, arising, eating, walking, hygiene, reach, grip, and common daily activities. Subjects are required to indicate the degree of difficulty they have experienced in each domain in the past week on a 4-point scale that ranges from 0 (without difficulty) to 3 (unable to do). Any individual score of less than 2 is adjusted to 2 if the activity requires assistance from another individual or the use of an assistive device. The

highest score in each category is then summed (0 to 24) and divided by the number of categories scored to give a score that ranges from 0 to 3 (Matsuda et al, 2003).

If the patient does not provide an answer for any questions within a category, no score will be provided for that category. The HAQ disability index will be calculated by dividing the sum of the category scores by the number of categories with at least 1 question answered. If fewer than 6 categories have responses, no disability score will be calculated. A lower HAQ disability score indicates an improvement in function.

Percent of subjects achieving HAQ-DI MCID

At a given visit a subject will be considered to have the minimum clinically important difference in HAQ-DI for PSA subjects if the difference is ≥ 0.3 points (Meese, 2009). Tables will present Observed case and NRI imputed data.

For further details for the analysis of this data, please refer to Section 8.3.9.

Additionally, a line plot will be generated to present change from Baseline in HAQ-DI score by randomized treatment group through Week 24/52.

8.3.15 Disease Activity Score DAS28(CRP) (28 joints evaluation)

The DAS28(CRP) will be calculated using CRP (mg/L) (see Table 10-1) and the Patient's Global Assessment of Disease Activity (VAS) (see Section 8.3.12). The joint assessment utilized for the DAS calculation will be based on 28 of the joints assessed for the 66/68-joint assessments (see Protocol Section 9.7.3)

- Upper extremity (26): bilateral shoulders, elbows, wrists (includes radiocarpal, and carpal and carpometacarpal bones considered as a single unit), MCP I, II, III, IV, and V, thumb interphalangeals (IP), PIP II, III, IV, and V
- Lower extremity (2): knees

using the same 2-point scale for the assessment of swelling and tenderness of each joint.

DAS28(CRP) is calculated as follows:

$$DAS28(CRP) = 0.56x\sqrt{TJC} + 0.28x\sqrt{SJC} + 0.014xPGADA + 0.36x\ln(CRP + 1) + 0.96$$

where TJC=tender joint count and SJC=swollen joint count.

The DAS28(CRP) will be evaluated for subjects with psoriatic arthritis (PsA). The analysis will be based on the PsA Set including only subjects with 3 or more tender joints and 3 or more swollen joints at Baseline on Observed case and LOCF imputed data.

- If there are missing observations for tender or swollen joints, then the remaining observations will be assessed and weighted by dividing by number of non-missing and by multiplying by 28.
- If a joint is not evaluable at Baseline, then that joint is set to missing throughout the study.
- If at least 1 item of DAS28(CRP) is available for a visit, LOCF will be applied to impute values of those individual components which are missing.
- For CRP values below the lower limit of quantification, half the lower limit will be used as the imputed value. The lower limit of quantification may vary depending on the assay used and the imputed value will vary with it. For example, if the value is

presented as <3.0 , then 1.5 will be used and if <0.1 is presented, then 0.05 will be used.

The DAS28(CRP) Disease Activity Classification will be presented in the categories Remission: <2.6 , LDA: ≥ 2.6 to ≤ 3.2 , MDA: >3.2 to ≤ 5.1 , HDA: >5.1 and Missing by visit and by randomized treatment group during Initial Period and by blinded maintenance or escape maintenance treatment group during Maintenance Period in Observed case data.

A line plot will be generated to present change from Baseline in DAS28(CRP) score by randomized treatment group through Week 24/52.

8.3.16 mNAPSI (change from Baseline)

Subjects with psoriatic nail disease will have a single target nail selected at the Baseline visit for evaluation using the modified Nail Psoriasis Severity Index (mNAPSI). The analysis of mNAPSI will be based on the Napsi Set (NAPSIS) on Observed case and LOCF imputed data. The nail selected at Baseline should be the most affected nail observed and should be the only one assessed during study. The target nail will be scored (0-3) for onycholysis/oil drop dyschromia, nail plate crumbling, and for pitting and will be scored (0 for “no” or 1 for “yes”) for leukonychia, nail bed hyperkeratosis, splinter hemorrhages, and red spots in the lunula.

A mNAPSI score will be derived by summing up each of the 7 items (Score Range = 0 to 13). If 1 response item scored on the 0 to 3 scale is missing, the missing response will be substituted by the average of the 2 available responses. If 1 or 2 response items scored on the 0 to 1 scale are missing, the missing response(s) will be imputed by the average of the available responses. Otherwise, the mNAPSI will be set to missing.

Tables for the absolute values and changes vs. Baseline will be provided by visit and by randomized treatment group for the Initial Period and by blinded maintenance treatment group or escape maintenance treatment group for the Maintenance Period. The treatment differences vs. PBO (LSMeans, 95% CI, p-value) are estimated at every visit during Initial Period, using an ANCOVA model with treatment and prior biological exposure (yes, no) as factors and Baseline score as covariate.

